### Blood specimen collection

- **BDNF assessment:** Blood specimens will be obtained immediately before and after AEx on three separate occasions (sessions 1, 9, and 18). A nurse from the South Carolina Clinical and Translational Research Institute (SCTR) will conduct all blood specimen collections. Briefly, an intravenous catheter will be placed in a superficial forearm vein at the beginning of the experimental session and will be maintained patent using an isotonic saline solution. Baseline blood samples will be drawn after a 30-minute equilibration period and will be drawn immediately before exercise commences. Immediate post-exercise blood samples will be taken within sixty seconds of exercise completion while the participant remains seated in the cycle ergometer. Blood samples will be collected into serum-separating tubes (SST) containing gel and clot activator and Ethylenediametetraacetic acid (EDTA) tubes and will be processed by The South Carolina Clinical and Translational Research Institute's Laboratory and Bio-repository. The purpose of collecting samples into SST and EDTA tubes will be to allow for assays for serum and plasma BDNF to be performed. Samples will be processed according to manufacturers recommendations. Enzyme-linked immunosorbent assays (Quantikine, R&D Systems, Minneapolis, MN) will be performed, in duplicate, to determine the concentration of serum and plasma BDNF. Serum and plasma BDNF will be assayed so that we may more completely describe

exercise-induced changes in BDNF. Recent work suggests reporting both serum and plasma to account for the potential of platelet activation to overestimate the effect of exercise on serum BDNF.

### **Intervention visits**

The AEx + DDP intervention will be a total of 18 sessions to be completed within 7 weeks. Each week, subjects will attend up to 3 sessions of AEx + DDP on non-consecutive days (M, W, F). It is expected that AEx + DDP sessions will last approximately 90 minutes. Post assessment visits will occur after the completion of 18 AEx + DDP session or 7 weeks, whichever occurs first.

**AEx:** Aerobic exercise will be performed on a recumbent stationary cycle (Monark 837e). During AEx, heart rate, blood pressure, and rate of perceived exertion (RPE) will be assessed at baseline, every 5 minutes during exercise (or sitting), immediately post-exercise, and then 5 minutes post-exercise. Exercise intensity will be determined using the Karvonen equation. The Karvonen equation uses an individual's maximum heart rate (MHR) and resting heart rate (RHR) to calculate heart rate reserve (HRR) using the equation:  $HRR = (MHR) - RHR$ . The MHR for each subject will be determined during his/her exercise tolerance test. An exercise physiologist will oversee each AEx session. The target intensity of each AEx session will be 70% HRR and will remain constant throughout the intervention. This intensity was selected for the 'priming' bout of AEx as preliminary results from our lab have shown it has a substantial impact on neuroplastic potential (See Figure 1.a) and serum BDNF in control subjects.

**DDP:** A therapist will oversee the patient's safety and progress during DDP by: (1) monitoring patient compliance and performance via metrics provided by the Microsoft Kinect system, (2) determining session parameters for all DDP sessions, and (3) continuously monitoring the patient to assess fatigue/pain, answer questions, and problem solve any issues. DDP will be dosed based on the number of repetitions performed. A repetition is recorded when the player moves his/her arm so that the avatar leaves a start position. The goal dose for subjects will be 200 repetitions per DDP session. The number of repetitions was selected because subjects enrolled in our previous studies have averaged 200 self-selected repetitions per day, achieved in ~1 hours without adverse event. Birkenmeir et al (2010) demonstrated that subjects with chronic stroke could safely obtain 200-300 arm movement repetitions in a 1-2 hour therapy session. The therapist overseeing DDP will be permitted to reduce the dose if a subject reports substantial fatigue or pain.

**Participant remuneration:** Study subjects will be paid \$25 per study visit. Subjects may attend up to a total of 23 study visits thus may receive up to \$575 of total compensation for participating in the study. Payments to subjects will be made via ClinCard. Subject will have \$25 added to their ClinCard for each study visit attended.

## **10.0 Specimen Collection and Banking**

Blood specimens will be collected as part of the study procedures. The specimens collected will be used to assess serum and plasma BDNF. Blood samples will be processed and stored by The South Carolina Clinical and Translational Research (SCTR) Institute's Laboratory and Bio-repository at MUSC. The specimens will be transported to the SCTR Research Laboratory in a clearly marked biohazard container by study staff or a SCTR nurse. The PI and SCTR Research Laboratory staff will have access to the specimens and associated data. Specimens will not be banked for future use after processing and analysis is completed.

## **11.0 Data Management**

**Power Analysis:** Although the primary goal of this proposal is to demonstrate feasibility and tolerability of AEx+DDP, the sample size is based on change in FMA-UE scores from recent work from Linder and colleagues. These data, for individuals with moderate UE impairment (the target sample of this study) yielded a FMA-UE mean change score of 12.3 for AEx + UE task practice and a FMA-UE mean change score of 4.4 for UE task practice only. Assuming the difference in mean FMA-UE change scores of 7.9 (pooled SD of 4.25), a sample size of n=5 for each group (AEx+DDP and DDP only) achieves 80% power with alpha = 0.05. Although we will not enroll a DDP-only group, we will be able to compare AEx+DDP to historical controls from the Co-I's lab. Two trials involving DDP have data from large samples (n=66 and n=103) providing ample data for comparison of AEx+DDP to DDP. Considering recruitment rates from the Co-I's previous trials (2-5 subjects/month) and anticipating a 20% dropout rate will inflate the sample size to n=10. Given recruitment rates and the timeline of this proposal (1 year) achieving this sample size appears feasible. This sample size is comparable to published literature and is sufficient to detect a large effect of AEx+DDP on FMA-UE compared to historical controls receiving DDP only. Additionally, this sample will provide a robust pilot data set for calculating effect sizes to power future trials examining AEx as primer for UE motor rehabilitation.

**Statistical Analysis Plan:** Feasibility and tolerability metrics of adherence, retention, and acceptability will be assessed (Aim 1). FMA-UE, WMFT, and SIS data will be compared to historical control data from previous DDP trials from [name] lab (Aim 2). We will utilize ANOVAs to test the effect of adding AEx to DDP on the mean FMA-UE, WMFT, and SIS-hand item rating and the average SIS-recovery scores (PROC GLM, SAS v9.4). Additionally, data describing the effect of AEx+DDP on UE impairment and function will be used to generate effect sizes for future research proposals. Pre- and post intervention PAS assessment will be tested with a student's T-test or Wilcoxon rank-sum test based on distributional assessment. The acute (within session) and training (over the course of intervention) effect of AEx on BDNF and DDP on CME will be assessed with a generalized mixed model analysis (PROC MIXED). Relationships of biomarkers of plasticity (PAS, BDNF, CME) and response to AEx+DDP (change in FMA-UE or WMFT) will be explored with Pearson or Spearman-rank order correlational analysis, depending on distributional assessment (Aim 3).

**Confidentiality:** All records regarding participation in this study will be kept in locked file cabinets in the appropriate laboratories and/or offices, and stored on MUSC network storage. Access to linked identifiers is limited to research personnel intimately involved with the human subjects. All data and records acquired from subjects is for research purposes only and will be kept confidential and maintained in a secure database identifiable only by subject code. The results of the study may be published for scientific purposes; however, subjects' identities will not be revealed and data will not be traceable to any individuals in any resultant publications. The information gathered during this study will be kept confidential to the extent permitted by law.

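### The sample-size paragraph does not lead from 5 to 10 by way of 20% dropout, names no test for its 80% power, and powers a two-group comparison that will not be run

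*Combined protocol and SAP*

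**What the plan says.** The Power Analysis in section 11.0 acknowledges that feasibility and tolerability are the primary goal, but states that "the sample size is based on change in FMA-UE scores". From one cited study it takes mean changes of 12.3 and 4.4 points, a difference of 7.9 with pooled SD 4.25, and concludes that "a sample size of n=5 for each group (AEx+DDP and DDP only) achieves 80% power with alpha = 0.05". No test and no sidedness are given.

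The next sentences change the design: "Although we will not enroll a DDP-only group, we will be able to compare AEx+DDP to historical controls". The available data are described as follows: "Two trials involving DDP have data from large samples (n=66 and n=103". Ten is then reached by citing past recruitment of 2 to 5 subjects a month and by "anticipating a 20% dropout rate will inflate the sample size to n=10". On the historical comparison, the paragraph says only that the sample "is sufficient to detect a large effect of AEx+DDP on FMA-UE compared to historical controls receiving DDP only".

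The Statistical Analysis Plan in the same section states the Aim 2 test: "We will utilize ANOVAs to test the effect of adding AEx to DDP on the mean FMA-UE, WMFT" and the SIS scores. It does not say whether FMA-UE enters as a change or as a score, or how the two historical trials are combined. Section 5.0 fixes total accrual at ten.

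**The concern.** The paragraph gives three figures in sequence (5 per group, 80% power, 10 enrolled), and a reader should be able to get from each to the next. The step from 5 to 10 fails on simple arithmetic. The 80% depends on a method that is not named, and the two-sided form of the ANOVA that the plan does name falls short of it at 5 per group. The calculation also describes a balanced comparison of two enrolled groups, whereas the trial will set one small group beside much larger historical cohorts.

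What is at stake is the Aim 2 detection claim. As written, nobody can tell what difference the real comparison could detect, or whether the power statement and the ANOVA use the same form of FMA-UE. Aim 1, the primary aim, does not depend on these figures.

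**Working it through.** **Inputs** (section 11.0, Power Analysis): difference 12.3 − 4.4 = 7.9; SD 4.25; alpha 0.05; power 80%; dropout 20%; historical cohorts 66 and 103 (66 + 103 = 169 if pooled, which the plan does not state). Standardised difference: 7.9 / 4.25 = 1.859. Equal SDs in both groups are assumed throughout.

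**1. The plan's own figure.** Two-sided normal approximation: n = 2 × [(1.960 + 0.842) × 4.25 / 7.9]² = 4.54, so 5 per group. The stated 5 is reproduced.

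**2. Dependence on the unstated test.** For t-tests, power comes from the noncentral t with 2n − 2 degrees of freedom and noncentrality 1.859 / √(2/n).

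| Method | Power at 5 per group | n per group for 80% |
|---|---|---|
| Two-sided normal approximation | 83.6% | 5 |
| One-sided t-test | 84.9% | 5 (4 gives 75.0%) |
| Two-sided t-test, equivalent to a two-group ANOVA | 73.1% | 6 (82.6%) |

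For the last row at n = 5, noncentrality is 1.859 / √0.4 = 2.94 against a critical value of 2.306 on 8 degrees of freedom.

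**3. Dropout.**
- From 5: 5 / (1 − 0.20) = 6.25, so 7.
- From 6: 6 / 0.80 = 7.5, so 8.
- Dropout needed to turn 5 into 10: 1 − 5/10 = 50%.
- Ten enrolled less 20%: 10 × 0.80 = 8 evaluable.

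The recruitment rates do not supply the missing step. Over the one-year timeline they give 12 × 2 = 24 to 12 × 5 = 60 subjects. If about two months are set aside for the last subject's roughly eight weeks of participation (section 9.0), they give 10 × 2 = 20 to 10 × 5 = 50. Either range shows that ten is achievable; neither produces ten.

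**4. The comparison that is planned.** Eight evaluable subjects against m historical controls, two-sided alpha 0.05. The standard error in SD units is √(1/8 + 1/m), and the detectable difference is solved from the noncentral t on m + 6 degrees of freedom.

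| Historical controls | Standard error (SD units) | Detectable at 80% | Points at SD 4.25 | Power for 7.9 points |
|---|---|---|---|---|
| 66 | 0.374 | 1.06 SD | 4.5 | 99.8% |
| 103 | 0.367 | 1.04 SD | 4.4 | 99.9% |
| 169 (pooled) | 0.362 | 1.02 SD | 4.3 | 99.9% |

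If the two cohorts enter as separate groups and AEx+DDP is contrasted with their average (1 df), the standard error is √[1/8 + ¼(1/66 + 1/103)] = 0.362, which again gives 1.02 SD, or 4.3 points. A 2-df omnibus F test over the three groups needs 1.13 SD (4.8 points at SD 4.25, historical means taken as equal), but the stated target, the effect of adding AEx to DDP, is a single contrast.

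**5. Why the form of the outcome matters.** The SD of 4.25 belongs to change scores. Against the same cohorts, 7.9 points stays detectable at 80% only up to an SD of 7.9 / 1.063 = 7.4 (66 controls) to 7.9 / 1.019 = 7.8 (169 controls). The documents give no SD for FMA-UE scores and none for the historical DDP trials.

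**The case against.** The best defence is that nothing practical turns on this. The study is a feasibility pilot and says so. Five per group does reproduce under a common formula. Given the plan's assumed effect and SD, even 5 evaluable subjects against 66 controls have 97.7% power, so the claim to detect a large effect is true on those assumptions. All of this stands, and it is why the point is minor. It does not mend the dropout step, which no choice of test can rescue, and it does not supply the missing detectable difference. Nor does reading 10 as two groups of 5 help, because only one group is enrolled and the text attributes the increase to dropout.

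A reader might infer three stronger things, and the documents support none of them:

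- *That n=5 is simply wrong.* It follows from a two-sided normal approximation or a one-sided t-test. The fault is that the method is unstated.
- *That the trial is underpowered because 73.1% is below 80%.* That figure belongs to a 5-against-5 comparison that will not take place.
- *That the ANOVA uses a different outcome from the power calculation.* FMA-UE is named in both places, and the analysis plan defines response for Aim 3 as change. The Aim 2 wording is ambiguous rather than contradictory.

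**Conclusion.** The point holds, at minor severity. The move from 5 to 10 is an arithmetic error: 20% dropout gives 7 or 8. The 80% at five per group depends on the method, and under a two-sided t-test or ANOVA it is 73.1%, a shortfall of one subject per hypothetical group. The comparison actually planned has no stated power or detectable difference. The choice of historical cohort and the form of FMA-UE are missing detail rather than error.

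Enrolment of ten is not called into question. The figures of over 99% power and 4.3 to 4.5 detectable points assume that the SD of 4.25 carries over to both the new subjects and the historical trials, that 8 of ten are evaluable, and that the historical controls are comparable. The documents show neither the SD nor the comparability for the historical data, and none of these figures allows for bias from non-concurrent controls.

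**What to change.** Keep n=10, and keep the 7.9-point difference and SD 4.25 as the assumed effect. In the Power Analysis:

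1. Name the method and sidedness behind five per group, or correct it to six per group for a two-sided t-test or ANOVA.
2. Replace the dropout derivation with wording such as: *Ten will be enrolled; with 20% dropout, 8 are expected to be evaluable.* Add the sponsor's actual reason for ten.
3. Name the historical cohort or cohorts and state the detectable difference: *At two-sided alpha 0.05, 8 subjects against 66, 103 or 169 (pooled) historical controls give 80% power for about 1.06, 1.04 or 1.02 SD, which is 4.5, 4.4 or 4.3 FMA-UE points at a change-score SD of 4.25. This will be recalculated with the historical SD and does not allow for bias from non-concurrent controls.* If the cohorts are entered separately, specify the 1-df contrast (about 1.02 SD); use 1.13 SD only if an omnibus F test is intended.

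In the Statistical Analysis Plan, state that the FMA-UE comparison is on change scores, to match the power statement.

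The cost is one reworded paragraph and one added phrase. The sponsor must choose the cohort or cohorts and obtain the historical SD of change from the co-investigator's lab. The detectable difference may grow once that SD is used. Enrolment and assessments are unaffected.

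### The Aim 2 comparison with historical controls makes no allowance for differences between trials, so its intervals will be too narrow if mean change varies from trial to trial

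*Combined protocol and SAP*

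**What the plan says.** All of this is in the combined protocol and SAP, section 11.0 Data Management.

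- **No concurrent control.** The Power Analysis says so openly: "Although we will not enroll a DDP-only group, we will be able to compare AEx+DDP to historical controls from the Co-I's lab".
- **Source of controls.** It goes on: "Two trials involving DDP have data from large samples (n=66 and n=103) providing ample data for comparison of AEx+DDP to DDP".
- **Sample size.** It is derived as if for two concurrent groups, from a 7.9-point difference in mean FMA-UE change and a pooled SD of 4.25: "a sample size of n=5 for each group (AEx+DDP and DDP only) achieves 80% power with alpha = 0.05". Then, "anticipating a 20% dropout rate will inflate the sample size to n=10".
- **Analysis.** The Statistical Analysis Plan says "FMA-UE, WMFT, and SIS data will be compared to historical control data from previous DDP trials", and "We will utilize ANOVAs to test the effect of adding AEx to DDP on the mean FMA-UE, WMFT, and SIS-hand item rating". The SIS-recovery score is treated the same way, and the procedure named is PROC GLM.

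The section does not say which historical participants will be used or how the two trials will be combined. It names no source-trial factor, random trial effect, covariate, matching or discounting of the historical data.

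**The concern.** Every AEx+DDP participant is in the new study and every control is in an older one. The contrast therefore contains the effect of adding exercise plus any difference in mean change between studies, whether from case mix, calendar period, delivery or rating. An ANOVA with participant-level error measures only the spread between participants. If trial means differ, its standard error is too small, its interval too narrow, and its nominal 5% test rejects too often. Calling the control data ample suggests that numbers solve this, but numbers reduce only the participant-level part.

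The comparison is secondary, but it matters. It is the only planned test of the exercise effect on arm outcomes, the sample size rests on it, and the resulting effect sizes are meant to support future proposals.

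**Working it through.** **Inputs**

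- Difference 7.9, SD 4.25, n = 5 per group, alpha 0.05: section 11.0, Power Analysis. Sidedness is not stated; two-sided is assumed.
- Completers: 10 enrolled (section 5.0) with 20% dropout gives 10 × 0.80 = 8.
- Controls: 66 and 103 (Power Analysis). The sum, 169, assumes that both trials are used in full and pooled.
- Between-trial SD of true mean FMA-UE change, τ: not in the documents. Assumed values are 0, 0.5, 1 and 2 points.

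**Step 1. The plan's own figure.** Normal approximation: 7.9 / (4.25 × √(2/5)) = 2.94, and Φ(2.94 − 1.96) gives 83.6% power at 5 per group. The stated n reproduces (a noncentral t calculation gives 73.1%). The only variance used is the participant SD.

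**Step 2. Standard error under simple pooling.** 4.25 × √(1/8 + 1/169) = 1.54 points. The 8 new participants alone contribute 4.25/√8 = 1.50, so the size of the control group hardly matters.

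**Step 3. Add between-trial variance.**

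True variance = 1.538² + τ² × [1 + (66/169)² + (103/169)²] = 2.365 + 1.524 τ²

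The 1 in the bracket is the new study's own trial effect, 1/1.524 = 66% of the added variance. The remaining third comes from the two control trials.

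**Step 4. Real type I error.** 2 × [1 − Φ(1.97 × 1.538 / true SE)], checked by simulation with 20,000 runs per value:

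| τ (assumed) | True SE | Type I, formula | Type I, simulated | Type I if τ applies only between the control trials |
|---|---|---|---|---|
| 0 | 1.54 | 5% | 5.1% | 5% |
| 0.5 | 1.66 | 6.7% | 6.9% | 5.5% |
| 1 | 1.97 | 12.4% | 12.1% | 7.4% |
| 2 | 2.91 | 29.7% | 28.0% | 15% |

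The formula runs slightly high at τ = 2 because the pooled residual absorbs some between-trial spread. With all 10 completing, the formula gives about 7%, 14% and 33% at τ = 0.5, 1 and 2.

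**Step 5. Other readings of the plan, 8 completers.**

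- Three-level fixed source factor, new study against the average of the two trials: SE 1.54; type I error 6.7%, 12.2% and 29.4% at τ = 0.5, 1 and 2.
- One historical trial only: about 7%, 14% and 33–34%. The added variance here is 2τ², more than the pooled 1.524τ².

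The conclusion does not depend on which reading is right.

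**Step 6. Requiring both separate contrasts to be significant in the same direction.** In simulation the type I error is about 6% at τ = 1 and 15–16% at τ = 2. It stays above 5% because both contrasts share the new study's deviation.

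**The case against.** **Pooling is not stated.** A reader might infer that the plan merges 169 controls into one sample. The text lists two sample sizes and says no more; a three-level factor in PROC GLM would fit it equally well. This stands, so 169 is used here only as a worked assumption. Step 5 shows that the other readings give much the same result.

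**No between-trial SD is given.** A reader might infer that the p-values are definitely too small. The documents do not support that: at τ = 0 there is no inflation, at 0.5 it is slight, and nothing in them points to 2. Some features may limit drift. The controls come from the Co-I's own lab, FMA-UE and WMFT are scored from video by trained, blinded raters (section 9.0), and the repetition goal was set from the average in that lab's earlier studies. Other features point the other way. Earlier participants chose their own repetitions whereas this study sets a goal, and entry here requires a passed exercise tolerance test and a PHQ-9 of 4 or less. The documents do not say whether the earlier trials selected participants in this way. Zero is thus also an assumption, and the plan makes it silently.

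**Most of the excess is the ordinary limit of a non-concurrent control, which the protocol discloses.** This is correct, and the point is worded accordingly. Disclosing the design does not put the uncertainty into the interval.

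**The comparison decides little.** Feasibility is the primary objective and no decision rule uses this p-value. At the planned 7.9-point difference, even an SE of 2.91 gives 7.9/2.91 = 2.7. This limits the severity. The risk lies with smaller observed differences and with effect sizes carried forward as more precise than they are.

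**Conclusion.** The concern holds in conditional form. The planned ANOVA has participant-level error only, and treatment cannot be separated from study. If true mean FMA-UE change differs between trials, the interval is too narrow and the 5% test rejects too often. The size, 5% rising to 28–30% as τ goes from 0 to 2 points, rests on 8 completers, an SD of 4.25, 169 pooled controls and an assumed τ; it is a range, not an estimate.

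The documents do not show that pooling is planned, that inflation is certain, or that merging the two control trials is its main source. Nor would separate contrasts or a fixed trial term repair the error rate. The change is worth making before analysis, but it concerns Aim 2 only.

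**What to change.** In the Statistical Analysis Plan:

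1. State which historical participants are used, and report the AEx+DDP contrast with a 95% CI against each historical trial separately as well as pooled.
2. Add a sensitivity CI that includes between-trial SDs of 0.5 to 2 points, labelled as assumed. At 8 against 169, the half-width 1.96 × SE goes from 3.0 points at τ = 0 to 3.2, 3.9 and 5.7 at τ = 0.5, 1 and 2.
3. Show the difference between the two historical trials only as a rough guide to drift. It carries 1 degree of freedom (two-sided t critical value 12.7), so it cannot estimate τ usefully.
4. Treat the p-values as descriptive, and call the result supportive only if both separate contrasts agree: same direction, both 95% CIs excluding zero.
5. State that none of this removes the confounding of treatment with study.

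In the Power Analysis, soften the claim that the historical data are ample.

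The cost is two extra contrasts and one sensitivity table on data the Co-I's lab already holds, with no extra participants or visits. The downside is wider intervals and a more modest Aim 2 claim.
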